### **10.4. Quality Assurance**

To ensure compliance with GCP and all applicable regulatory requirements, GSK may conduct a quality assurance assessment and/or audit of the site records, and the regulatory agencies may conduct a regulatory inspection at any time during or after completion of the study. In the event of an assessment, audit or inspection, the investigator (and institution) must agree to grant the advisor(s), auditor(s) and inspector(s) direct access to all relevant documents and to allocate their time and the time of their staff to discuss the conduct of the study, any findings/relevant issues and to implement any corrective and/or preventative actions to address any findings/issues identified

### **10.5. Study and Site Closure**

The end of the study will occur when the last subject has completed the last visit, and all SAEs have been followed up as required.

Upon completion or termination of the study, the monitor will conduct site closure activities with the investigator or site staff (as appropriate), in accordance with applicable regulations, ICH GCP, and GSK Standard Operating Procedures (SOPs).

GSK reserves the right to temporarily suspend or terminate the study at any time for reasons including (but not limited to) safety issues, ethical issues, or severe noncompliance. If GSK determines that such action is required, GSK will discuss the reasons for taking such action with the investigator or head of the medical institution (where applicable). When feasible, GSK will provide advance notice to the investigator or head of the medical institution of the impending action.

If a study is suspended or terminated for **safety reasons**, GSK will promptly inform all investigators, heads of the medical institutions (where applicable), and/or institutions conducting the study. GSK will also promptly inform the relevant regulatory authorities of the suspension/termination along with the reasons for such action. Where required by applicable regulations, the investigator or head of the medical institution must inform the IRB/IEC promptly and provide the reason(s) for the suspension/termination.

GSK also reserves the right to close sites which fail to enroll subjects within a predefined timeframe, as described in the SPM.

## **10.6. Records Retention**

Following closure of the study, the investigator or head of the medical institution (where applicable) must maintain all site study records (except for those required by local regulations to be maintained elsewhere) in a safe and secure location. The records must be easily accessible when needed (e.g., for a GSK audit or regulatory inspection) and must be available for review in conjunction with assessment of the facility, supporting systems, and relevant site staff.

Where permitted by local laws/regulations or institutional policy, some or all of the records may be maintained in a format other than hard copy (e.g., microfiche, scanned, electronic); however, caution must be exercised before such action is taken. The investigator must ensure that all reproductions are legible and are a true and accurate copy of the original. In addition, they must meet accessibility and retrieval standards, including regeneration of a hard copy, if required. The investigator must also ensure that an acceptable back-up of the reproductions exists and that there is an acceptable quality control procedure in place for creating the reproductions.

GSK will inform the investigator of the time period for retaining the site records in order to comply with all applicable regulatory requirements. The minimum retention time will meet the strictest standard applicable to a particular site, as dictated by local laws/regulations, GSK standard operating procedures, and/or institutional requirements.

The investigator must notify GSK of any changes in the archival arrangements, including, but not limited to archival of records at an off-site facility or transfer of ownership of the records in the event that the investigator is no longer associated with the site.

## **10.7. Provision of Study Results to Investigators, Posting of Information on Publicly Available Clinical Trials Registers and Publication**

Where required by applicable regulatory requirements, an investigator signatory will be identified for the approval of the clinical study report. The investigator will be provided reasonable access to statistical tables, figures, and relevant reports and will have the opportunity to review the complete study results at a GSK site or other mutually-agreeable location.

GSK will also provide the investigator with the full summary of the study results. The investigator is encouraged to share the summary results with the study subjects, as appropriate.

Upon completion of the clinical study report, GSK will ensure public disclosure of the clinical trial research results via the GSK Clinical Study Register. GSK will also publish the results of the study to be searchable on the internet according to the GSK policy and SOP.

The results summary will be posted to the GSK Clinical Study Register no later than 8 months after the final primary completion date, the date that the final subject was examined or received an intervention for the purposes of final collection of data for the primary outcome. In addition, a manuscript will be submitted to a peer-reviewed journal for publication no later than 18 months after the last subject's last visit. When manuscript publication in a peer reviewed journal is not feasible, a statement will be added to the register to explain the reason for not publishing.

When manuscript publication in a peer-reviewed journal is not feasible, further study information will be posted to the GSK Clinical Study Register to supplement the results summary.

## **10.8. Safety Review Team**

The SRT includes GSK representatives from Biostatistics, Clinical and Global Clinical Safety and Pharmacovigilance. Representatives from other disciplines may be involved in the SRT meetings on an ad hoc basis as required to provide additional expertise. All members of the SRT must be independent of the LAP117314 study team, and must have no other role or responsibility within the broader scope of the study. The primary role of the SRT is to provide an internal and independent review of safety data to protect the interests of subjects and to ensure their safety.

The SRT will review safety data on an ongoing basis. The first formal review of safety data will be conducted after the first 60 subjects have received at least 9 weeks of treatment with lapatinib and capecitabine. Subsequent formal review will be conducted at least every 12 weeks, or more frequently if required. It is anticipated that the SRT will meet to conduct formal review of the safety data at least three times during the course of the study. Unblinded study data will be provided to the SRT by a statistician independent of the LAP117314 study team. All efforts will be made to maintain the study integrity and validity of study data.

## 12. APPENDICES

### 12.1. Appendix 1 Diarrhoea Management Guidelines

Experience thus far suggests that when lapatinib is used as monotherapy most diarrhoea presents as uncomplicated NCI CTCAE Grade 1 or 2 (G1 54%, G2 20%, G3 15%, G4<1%).

In rare cases, diarrhoea can be debilitating, and potentially life threatening if accompanied by dehydration, renal insufficiency, and/or electrolyte imbalances.

Standardised and universal guidelines have been developed by an American Society of Clinical Oncology (ASCO) panel for treating chemotherapy-induced diarrhoea [Benson, 2004]. Presented in the sections below are the recommended guidelines for the management of diarrhoea in subjects receiving lapatinib-based therapy; these guidelines were derived from the recommendations published by the ASCO panel [Benson, 2004].

Early identification and intervention is critical for the optimal management of diarrhoea. A subject's baseline bowel patterns should be established so that changes in patterns can be identified while subject is on treatment.

**It is strongly recommended to give subjects receiving lapatinib-based therapy a prescription of loperamide with instructions to start loperamide at the onset of diarrhoea as per the recommendations outlined below.**

**Subjects should be instructed to first notify their physician/healthcare provider at onset of diarrhoea of any severity.**

An assessment of frequency, consistency and duration as well as knowledge of other symptoms such as fever, cramping, pain, nausea, vomiting, dizziness and thirst should be taken at baseline. Consequently subjects at high risk of diarrhoea can be identified. Subjects should be educated on signs and symptoms of diarrhoea with instructions to report any changes in bowel patterns to the physician.

It is recommended that subjects keep a diary and record the number of diarrhoea episodes and its characteristics. They should also include information on any dietary changes or other observations that may be useful in the evaluation of their diarrhoea history.

If subjects present with diarrhoea of any grade, check they are taking lapatinib correctly, i.e. single daily dose, rather than splitting it through the day. . Obtain information on food (solid and liquid) and over the counter (OTC) medication, including herbal supplements, taken during the lapatinib treatment period.

## Definitions

National Cancer Institute (NCI) guidelines define diarrhoea compared to baseline ([Appendix 1 Table 1](#))

**Appendix 1 Table 1 NCI Common terminology criteria for grading diarrhoea adverse events (version 4.03)**

Adverse Event Grade	Diarrhoea
1	Increase of <4 stools/day over baseline; mild increase in ostomy output compared to baseline
2	Increase of 4-6 stools/day over baseline; moderate increase in ostomy output compared to baseline;
3	Increase of $\geq 7$ stools/day over baseline; incontinence; hospitalisation indicated; severe increase in ostomy output compared to baseline; limiting self care activities of daily living (ADL)
4	Life-threatening consequences; urgent intervention indicated
5	Death

**Uncomplicated diarrhoea** is considered mild-to-moderate and defined as CTCAE Grade 1 or 2 with no complicating signs or symptoms.

**Complicated diarrhoea** is severe and defined as any CTCAE Grade 3 or 4 diarrhoea, or Grade 1 or 2 with one or more of the following signs or symptoms:

- Moderate to severe abdominal cramping
- Nausea/vomiting  $\geq$ Grade2
- Decreased performance status
- Fever
- Sepsis
- Neutropenia
- Frank bleeding (red blood in stool)
- Dehydration

## Management Guidelines for Subjects Receiving Lapatinib Alone or as Combination Therapy

### A) Uncomplicated Diarrhoea

#### I. CTCAE Grade 1

**NOTE: Subject should be instructed to: start supportive care immediately at the first episode of diarrhoea (i.e., unformed stool) and call their physician.**

1. Administer loperamide

- a. Initial dose 4mg followed by 2mg after every unformed stool. Re-evaluate after 24 hours, if:
    - i. Diarrhoea is resolving:
      - Continue loperamide treatment at 2mg dose after every unformed stool until diarrhoea free (i.e., <Grade 1/bowel patterns returned to baseline) for 12 hours.
        - If diarrhoea recurs, re-initiate loperamide treatment as needed to maintain normal bowel patterns
    - ii. Diarrhoea is not resolving:
      - Administer loperamide at 2mg every 4 hours for the next 24 hour. Re-evaluate after 24 hours. If diarrhoea is resolving, administer loperamide at 2mg after every unformed stool until diarrhoea free (i.e., <Grade 1/bowel patterns returned to baseline) for 12 hours. If diarrhoea is not resolving continue loperamide treatment at 2mg every 4 hours and re-evaluate every 24 hours.
  - b. If Grade 1 diarrhoea persists for more than 1 week with loperamide treatment, consider treatment with second-line agents (octreotide, budesonide or tincture of opium).
2. Dietary modifications which are essential in the management of diarrhoea include the following recommendations (American Cancer Society; National Cancer Institute):
- a. Stop all lactose containing products and eat small meals
  - b. Avoid spicy, fried and fatty foods, raw vegetables and other foods high in fiber
    - i. Eat foods low in fiber (i.e., lean meat, rice, skinless chicken or turkey, fish, eggs, canned or cooked skinless fruits, cooked/pureed vegetables)
  - c. Avoid caffeine and alcohol as they can irritate the bowel and increase motility
  - d. Hydration: Drink 8-10 large glasses of clear liquids a day (e.g., water, electrolyte drink).
    - i. Avoid acidic drinks such as tomato juice and fizzy soft drinks
  - e. Supplement diet to include foods rich in potassium (e.g., bananas, potatoes, and apricots) , evaluate their impact on diarrhoea due to the fiber content (e.g., apricots)
1. Continue with study treatment (i.e., lapatinib-based treatment)

Continue with supportive care until diarrhoea has resolved (diarrhoea free for 12 hours/bowel pattern return to baseline). Once diarrhoea has resolved, the subject can begin to gradually re-introduce foods from their normal diet.

If diarrhoea recurs following stopping of loperamide treatment, resume loperamide treatment at the dose and schedule recommended above and re-introduce diet modifications. Continue with study treatment.

If Grade 1 diarrhoea persists for  $\geq 2$  weeks, refer to the management guidelines for Persistent Grade 2 Diarrhoea.

## II. CTCAE Grade 2

**NOTE: Subject should be instructed to call physician at first episode of diarrhoea and start supportive care immediately**

1. Administer loperamide
  - a. Initial dose 4mg followed by 2mg every 4 hours or after every unformed stool. Re-evaluate after 24 hours. If:
    - i. Diarrhoea is resolving, continue loperamide treatment at 2mg dose after every unformed stool until diarrhoea free (i.e., <Grade 1/bowel patterns returned to baseline) for 12 hours
      - If diarrhoea recurs, re-initiate loperamide treatment as needed to maintain normal bowel patterns
    - ii. Diarrhoea is not resolving, consider loperamide dose of 2mg every 2 hours for 24 hours. If Grade 2 diarrhoea persists after total of 48 hours of loperamide treatment, start second-line agents (octreotide, budesonide or tincture of opium).
      - Consider performing stool work-up, CBC, electrolytes and other tests as appropriate
2. Dietary modifications which are essential in the management of diarrhoea include the following recommendations (American Cancer Society; National Cancer Institute):
  - a. Stop all lactose containing products and eat small meals
  - b. Avoid spicy, fried and fatty foods, bran, raw vegetables and other foods high in fiber
    - i. Eat foods low in fiber (i.e., lean meat, rice, skinless chicken or turkey, fish, eggs, canned or cooked skinless fruits, cooked/pureed vegetables)
  - c. Avoid caffeine and alcohol as they can irritate the bowel and increase motility
  - d. Hydration: Drink 8-10 large glasses of clear liquids a day (e.g., water, electrolyte drink).
    - ii. Avoid acidic drinks such as tomato juice and fizzy soft drinks
  - e. Supplement diet to include foods rich in potassium (e.g., bananas, potatoes, and apricots), evaluate their impact on diarrhoea due to the fiber content (e.g., apricots)
2. Continue with study treatment (i.e., lapatinib-based treatment)

Continue with supportive care until diarrhoea has resolved (diarrhoea free for 12 hours/bowel pattern return to baseline). Once diarrhoea has resolved, the subject can begin to gradually re-introduce foods from their normal diet. Refer to Section IV “Recurrent Diarrhoea” for study treatment guidelines.

If diarrhoea recurs following stopping of loperamide treatment, resume loperamide treatment at the dose and schedule recommended above and re-introduce diet modifications.

**III. Persistent ( $\geq 3$  days/72 hours) Grade 2 Diarrhoea:** hold lapatinib and chemotherapy (if applicable) until diarrhoea resolves ( $<$ Grade 1/return to baseline bowel pattern). If supportive care measures and the interruption of study treatment (i.e., lapatinib and if applicable chemotherapy) are ineffective in treating persistent Grade 1 or Grade 2 diarrhoea, perform stool work-up, CBC, electrolytes and other tests as appropriate, consider consulting with a gastrointestinal specialist.

After diarrhoea resolves ( $\leq$ Grade 1), resume treatment with lapatinib and chemotherapy (if applicable).

**IV. Recurrent Diarrhoea (more than 1 occurrence of Grade 2 diarrhoea):** once the 2nd occurrence of Grade 2 diarrhoea resolves to  $\leq$ Grade 1, consider reducing the dose of lapatinib by 250mg or 1 tablet, unless the lapatinib dose already had been reduced to 750mg. No further dose reduction is recommended for subjects taking lapatinib at 750mg.

3. Consider a dose reduction for chemotherapy (if applicable)

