LAP117314 is an open label, randomised study to explore the potential benefit of the prophylactic use of octreotide in the prevention or reduction of diarrhoea associated with treatment with lapatinib and capecitabine. The primary endpoint of the study is investigator-reported diarrhoea with a severity of Grade 2 and above, as defined by the National Cancer Institute common terminology criteria for adverse events (NCI CTCAE), version 4.03. The definition of AEs in accordance with the NCI CTCAE criteria is consistent with the definitions used in previous studies of lapatinib in combination with capecitabine. Diarrhoea with a severity of Grade 2 or more has a significant effect on the tolerability of treatment, the acceptability of continued treatment, and the subject's sense of wellbeing. Management of Grade 2 diarrhoea includes treatment interruption for capecitabine when the first episode occurs, and treatment interruption for lapatinib after the second episode. Secondary endpoints include other aspects of the frequency and severity of diarrhoea of all grades of severity and of the consequences and management of diarrhoea, which will be recorded by the investigator using standard methodology and also by patient reported outcome (PRO) measures in the study-specific Diarrhoea Management Diary (DMD) and in the Functional Assessment of Chronic Illness Therapy-Diarrhoea (FACIT-D). Inclusion of PROs in this study provides an opportunity to contrast and compare outcomes reported by investigators and by subjects within each treatment group, although differences between the electronic Case Report Form (eCRF) data and the PRO data will preclude formal comparisons. Disease progression measured as overall response rate and clinical benefit response is a secondary endpoint.

The prevention of diarrhoea associated with cancer treatment has the potential to improve treatment compliance and to improve the patients' sense of wellbeing. LAP117314 will evaluate the efficacy of the prophylactic use of octreotide in the prevention or reduction of diarrhoea associated with treatment with lapatinib and capecitabine.

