Overall, 140 subjects will be enrolled. LAP117314 is an exploratory Phase II study, and the sample size is not based on the number of subjects required to achieve a pre-specified reduction in the control incidence of diarrhoea. While it is predicted that octreotide prophylaxis will reduce the frequency and severity of diarrhoea, the degree of benefit and the impact this might have on treatment compliance and on the subjects' quality of life are uncertain. The study should be of sufficient size to provide clinically meaningful data within a reasonable enrollment timeframe.

The primary endpoint of the study is the proportion of subjects reporting diarrhoea with a severity of Grade 2 or more. This represents an increase of at least four stools per day relative to baseline, and is considered to be sufficiently severe to have an impact on the subjects' sense of wellbeing. The recommended management of Grade 2 diarrhoea includes maintaining treatment with lapatinib on the first and second occurrence, with interruption of lapatinib treatment on subsequent occurrences ([Table 10](#)), and interruption

of treatment with capecitabine at the first occurrence, with restart at a reduced dose after the first occurrence if clinically indicated, restart at a reduced dose after the second and third occurrences, and treatment withdrawal after the fourth occurrence (Table 11). In addition to the diarrhoea management related dose interruptions, Grade 2 diarrhoea may also adversely affect the acceptability of subsequent cycles of treatment.

Secondary endpoints of the study provide a broader assessment of the incidence and severity of diarrhoea of all grades. It is possible that octreotide prophylaxis may not reduce the overall incidence of diarrhoea, but may reduce the severity of these incidences of diarrhoea. The proportion of subjects who report diarrhoea with a severity of Grade 3 or more will be summarised separately, as this represents diarrhoea which requires a significant clinical intervention.

The frequency and severity of diarrhoea will be recorded by the investigator in accordance with the standard process for AE reporting in the eCRF. In addition, actions associated with the management of diarrhoea (use of anti-diarrhoeal medication, unscheduled visits to healthcare professionals, treatment interruption, rehydration) will be recorded in the eCRF. This methodology is broadly consistent with that used in clinical studies EGF100151 and EGF111438.

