## **5. STUDY TREATMENTS**

The term 'study treatment' is used throughout the protocol to describe any combination of products received by the subject as per the protocol design. Study treatment may therefore refer to the individual study treatments or the combination of those study treatments.

The mechanism for providing lapatinib and capecitabine will vary by centre and by country, depending on drug reimbursement status. Lapatinib and capecitabine will be provided locally by each centre, and if this is not possible lapatinib and capecitabine will be provided by GSK. Only subjects enrolled in the study may receive study-related treatment, in accordance with all applicable regulatory requirements. Only the site pharmacist or authorized site personnel may supply or administer study-related treatment.

Octreotide will be provided by GSK for all sites.

Prescribing information and patient information documents for lapatinib, capecitabine and octreotide will be sourced locally, in the local language.

The content of the treatment labels will be in accordance with all applicable regulatory requirements. A Material Safety Data Sheet describing the occupational hazards and recommended handling precautions will be provided to site staff if required by local laws or will otherwise be available from GSK upon request. Under normal conditions of handling and administration, study-related treatment is not expected to pose significant safety risks to site staff.

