**Table 11 Dose modification rules for capecitabine**

Toxicity NCI-CTCAE Grade	During Course of Therapy	Capecitabine Dose Change
Grade 1	Maintain dose	No change
Specific Events of Grade 2/3 Haematology ANCs $<1.5 \times 10^9/L$ Platelet count is $<100.0 \times 10^9/L$ Haemoglobin is $<9.0$ g/dL (after transfusion if needed) Chemistry For liver AE refer to Section 5.13. Serum Creatinine $\geq 1.5$ mg/dL. Calculated Creatinine Clearance $<40$ mL/mins (Appendix 6)	Interrupt treatment until resolved to Grade 0-1, up to 14 days.  If toxicity does not resolve, consult GSK Medical Monitor to determine if it is in the best interest of the subject to continue in the study.	1 st appearance -Resume at 100% or Resume at 75% (rounded to nearest 150mg) as clinically indicated 2 nd appearance Resume at 75% (rounded to nearest 150mg) 3 rd appearance-Resume at 50% of starting dose rounded to nearest 150mg) 4 th appearance-Discontinue permanently
Grade 2-Any other event For liver AE refer to Section 5.13. For diarrhoea refer to Section 5.12.2 and to Appendix 1	Interrupt treatment until resolved to Grade 0-1, up to 14 days.	1 st appearance -Resume at 100% or Resume at 75% (rounded to nearest 150mg) as clinically indicated 2 nd appearance Resume at 75% (rounded to nearest 150mg) 3 rd appearance-Resume at 50% of starting dose rounded to nearest 150mg) 4 th appearance-Discontinue permanently
Grade 3 – Any other event For liver AE refer to Section 5.13. For diarrhoea refer to Section 5.12.2 and to Appendix 1	Interrupt until resolves to Grade 0-1, up to 14 days.	1 st appearance-Resume 75% of starting dose (rounded to nearest 150mg) 2 nd appearance- Resume 50% of starting dose (rounded to nearest 150 mg) 3 rd appearance- Discontinue treatment permanently
Grade 4 For liver AE refer to Section 5.13. For diarrhoea refer to Section 5.12.2 and to Appendix 1	Interrupt until resolves to Grade 0-1, up to 14 days.	Consult GSK Medical Monitor to determine if it is in the best interest of the subject to continue at a dose level lower than the original capecitabine dose

Toxicity grading system according to NCI-CTCAE V4.03

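### At a first uncomplicated Grade 2 diarrhoea episode, Appendix 1 reads as continuing capecitabine for up to 72 hours while Table 11, Section 3.2 and the Summary interrupt it at once; the lapatinib rules for Grade 4 also conflict.

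*Protocol*

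**What the plan says.** Four places in the protocol deal with capecitabine at a first Grade 2 diarrhoea episode.

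- Section 5.11, Table 11, row for other Grade 2 events: "Interrupt treatment until resolved to Grade 0-1, up to 14 days". The restart doses begin with the first appearance, so the interruption covers it.
- Section 3.2 applies Tables 10 and 11 by name to Grade 2 diarrhoea. Lapatinib is maintained at the first two occurrences, and there is interruption "of treatment with capecitabine at the first occurrence".
- Protocol Summary, Rationale: "treatment interruption for capecitabine when the first episode occurs".
- Appendix 1, uncomplicated Grade 2: "Continue with study treatment (i.e., lapatinib-based treatment". Subsection III, for Grade 2 lasting 72 hours or more: "hold lapatinib and chemotherapy (if applicable) until diarrhoea resolves".

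The cross-references are mutual. The Table 11 row says: "For diarrhoea refer to Section 5.12.2 and to Appendix 1". Section 5.12.2.2 says the Appendix 1 guidelines are to be used together with Sections 5.10 and 5.11. The Summary's Study Design text bases dose modification and interruption on the two product SPCs, without placing them above or below either source.

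For Grade 4, Appendix 1 discontinues lapatinib and holds chemotherapy. Table 10 interrupts lapatinib for up to 14 days and leaves continuation at a reduced dose to consultation with the Medical Monitor. Under Section 4.3.2, permanent discontinuation of either drug stops both and withdraws the subject.

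**The concern.** A site cannot stop and continue the same drug at the same moment. Two sites could handle the same first Grade 2 episode differently, one withholding capecitabine and the other giving it at full dose for up to three days, and both could point to the protocol. At Grade 4, the choice of page decides whether a patient can return to lapatinib at all. Diarrhoea is the condition under study, and Section 3.1 calls adherence to the design requirements essential, so this is a poor place for two rules. At stake are patient safety and the meaning of the compliance and dose-interruption summaries in SAP Sections 2.4.1, 2.6.1.4 and 2.7.1.2.

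**Working it through.** The plan gives no figure on this point, so the check is a reading of the texts followed by a dose count.

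1. **Does study treatment in Appendix 1 include capecitabine?** Section 5 says the term "is used throughout the protocol to describe any combination of products received by the subject". Its next sentence adds that it may mean the individual treatments or the combination, so the definition alone settles nothing. Appendix 1 subsection III speaks of "the interruption of study treatment (i.e., lapatinib and if applicable chemotherapy", and the guidelines are titled as covering lapatinib alone or in combination. If capecitabine were already off from onset, the instruction to hold chemotherapy at 72 hours would have nothing left to do. The most natural reading is that capecitabine continues until then. A lapatinib-only reading is permitted but strained.

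2. **Does any text rank the sources?** Table 11 sends diarrhoea to Appendix 1, Section 5.12.2.2 sends the reader back to Table 11, and the SPCs are a third, unranked authority. The Appendix 1 algorithm figure is not shown in the text available, and the Study Procedures Manual is a separate document. The finding is therefore that no visible text ranks them.

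3. **Grade 4.** Discontinuing lapatinib and interrupting it with possible return at a reduced dose are different outcomes. Table 10's Grade 4 row points diarrhoea to Appendix 1 but also states its own rule. Section 4.3.2 widens the gap: if Appendix 1 means permanent discontinuation, capecitabine stops too.

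4. **Size of the Grade 2 difference.** Section 5.2.1 gives capecitabine twice daily for 14 of every 21 days.
   - Doses per cycle: 2 × 14 = 28.
   - Doses in 72 hours: 3 days × 2 = 6.
   - Share of the affected cycle: 6/28 = 21.4%.
   - Share of the first 3 cycles: 6/84 = 7.1%.
   - Share of 24 weeks (8 cycles): 6/224 = 2.7%.

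   These are upper limits for one episode falling wholly on dosing days. They do not count any dose reduction at restart.

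5. **Patients affected.** The nearest proxy in Section 1.1 is a maximum severity of Grade 2: 38/269 = 14.1% in EGF111438 and 48/210 = 22.9% in EGF100151. It errs both ways. It includes complicated Grade 2 (where Appendix 1 holds both drugs), onsets in the off-capecitabine week, and late onsets. It omits Grade 3 patients who passed through Grade 2 first. Grade 4 was 2 of 210 in EGF100151. The number of Grade 2 episodes lasting 72 hours cannot be derived.

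6. **Endpoints.** A patient with Grade 2 diarrhoea in the first 9 weeks is already a primary-endpoint event, whatever is then done with capecitabine. The protocol's endpoint on diarrhoea-related dose changes is not in SAP Table 1-3. The compliance and interruption summaries that remain are descriptive.

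**The case against.** The best defence is that the texts can be combined, as Section 5.12.2.2 asks. Table 10 keeps lapatinib going at a first Grade 2 episode, which matches the Appendix 1 line if that line means lapatinib only, and Section 5 allows study treatment to mean a single drug. Table 11 then adds the capecitabine interruption. Three consistent, drug-specific statements stand against one generic line in guidelines that call themselves recommended and that subjects are encouraged to follow. This shows that the intended rule can probably be recovered. It does not remove the instruction a site would meet in Appendix 1, whose own gloss of study treatment includes chemotherapy.

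A reader might infer that Section 1.3.1 makes Appendix 1 binding, because it says diarrhoea is to be managed under those guidelines. That sentence belongs to a paragraph on octreotide-associated gastrointestinal events and is weak authority for capecitabine dosing.

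A reader might also infer that Appendix 1 and the tables contradict each other throughout. They do not:

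- The 72-hour lapatinib hold can be layered on Table 10.
- The lapatinib reduction after a second Grade 2 occurrence is only something to consider.
- After Grade 3, a reduced lapatinib dose is one of Table 10's options, and Table 11's 75% restart satisfies the advice to consider reducing chemotherapy.

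**Conclusion.** Wrong as written, of minor severity. Two conflicts stand: capecitabine at a first uncomplicated Grade 2 episode, and lapatinib at Grade 4. The first rests on reading study treatment in Appendix 1 as its subsection III glosses it; Table 11 is probably what was meant. The difference is at most 6 doses per affected episode: 21% of that cycle and 2.7% over 24 weeks. The 2.7% assumes eight full cycles and that held days count as planned dose, which the SAP does not say.

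A reader might infer that the primary result or the comparison between arms is distorted. The documents do not support that: the primary event has already occurred when the rules diverge, and both arms work under the same text. Nor do they show that up to 72 hours of continued capecitabine with loperamide causes harm. The safety point is that dosing in active Grade 2 toxicity should not depend on which page a site consults.

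**What to change.** - **Section 5.12.2.2:** state that Table 11 governs capecitabine for diarrhoea, with interruption from the first Grade 2 episode, and that Appendix 1's 72-hour lapatinib hold applies in addition to Table 10.
- **Appendix 1, Grade 2:** replace the line quoted above with an instruction to continue lapatinib and interrupt capecitabine per Table 11.
- **Grade 4:** adopt the more cautious Appendix 1 rule. Say that lapatinib discontinuation is permanent, so both drugs stop under Section 4.3.2, and amend Table 10's Grade 4 row for diarrhoea. Table 11's Grade 4 row, which allows a lower capecitabine dose after consultation, and Appendix 1's chemotherapy hold need the same alignment.
- **Sites:** notify them by the letter route already provided in Section 5.12.

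The cost is protocol wording and one letter, with no added data or visits.
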